11.3 Multiple Comparison / Multiplicity

The primary and key secondary endpoints will be tested among the subgroups of tBRCA, HRD, and ITT using the ordered step-down procedure as illustrated in Figure 1 below.

11.4 Examination of Efficacy in Subgroups

Subgroup analyses of the primary endpoint (invPFS) will be presented for the following:

- Randomization stratification factors
 - tBRCA, nbHRD, or biomarker negative as determined by CTA for randomization (per gene list, as defined in Appendix A)
 - Interval between completion of the penultimate platinum-based regimen and disease progression (6 to 12 months or > 12 months)
 - Best response (RECIST CR or PR [RECIST and/or GCIG CA-125 response]) to platinum regimen received immediately prior to initiation of rucaparib maintenance therapy

- HRD definition used for analysis (tBRCA, non-tBRCA LOH+, non-tBRCA LOH-, non-tBRCA LOH unknown), as further described in Section 3.3
- Age groups (< 65, 65-74, \geq 75)
- Race (white, non-white)

Subgroups by Disease Burden at Baseline:

In addition, the primary endpoint (invPFS) will be further explored based on the disease burden at baseline in the following subgroups of patients:

- **Measurable Disease**: All patients who have measurable disease (i.e., target lesion of any size) at baseline as assessed by the investigator and/or independent radiology reviewer).
- **No Disease**: All patients who have no target lesions or non-target disease at baseline as assessed by the investigator and/or independent radiology reviewer).
- No Bulky Disease: All patients with any/all lesions < 2 cm in the shortest axis (lymph nodes) or longest axis (all other lesions) as assessed by the independent reviewer. A reassessment of baseline scans was conducted by independent radiology reviewer in order to define this subgroup. The shortest axis is used as the diameter for malignant lymph nodes, and the longest axis is used for all other measurable lesions, in accordance with RECIST 1.1.

Subgroups Based on Gene Mutation and Type:

In addition, the primary endpoint (invPFS) will be further explored based on mutation and mutation type.

- BRCA mutation (*BRCA1*, *BRCA2*)
- BRCA mutation origin (germline, somatic, unknown)
- Patients with tumors harboring a deleterious mutation within the pre-specified list of non-BRCA HRR genes This pre-specified list of non-BRCA HRR genes was derived based on biomarker analysis of ARIEL2, and is more specific than the nbHRD gene list used for stratification.
- Combining the somatic tBRCA subgroup with the non-tBRCA LOH+ subgroup.
- Comparing germline tBRCA vs all others (i.e., all non-germline tBRCA and non-tBRCA patients)

In addition, a sensitivity analysis of invPFS will be performed for all BRCA patients, including those identified as BRCA by the CTA and those identified by a local or central BRCA test.

12 SAFETY ANALYSIS

The safety analyses will be performed using the safety population.

12.1 Adverse Events

AEs will be classified using the MedDRA version 19.1 classification system. The severity of the toxicities will be graded according to the National Cancer Institute Common Terminology Criteria for Adverse Events (NCI CTCAE) whenever possible. Treatment-emergent adverse events (TEAEs) are defined as AEs with onset date on or after the date of first dose of study medication until the date of the last study medication dose plus 28 days. AEs will be considered treatment-emergent if all or part of the date of onset of the adverse event is missing and it cannot be determined if the AE meets the definition for treatment-emergent.

The number and percentage of patients who experienced TEAEs for each SOC and PT will be presented. Multiple instances of the TEAE in each SOC and multiple occurrences of the same PT are counted only once per patient. The number and percentage of patients with at least one TEAE will also be summarized.

Separate tables will be presented as follows:

- All TEAEs;
- TEAEs by CTCAE grade;
- Grade 3 or greater TEAEs;
- Treatment-related TEAEs;
- Serious TEAEs;
- TEAEs with an outcome of death;
- TEAEs leading to discontinuation of study medication;
- TEAEs resulting in reduction study medication;
- TEAEs resulting in interruption of study medication;
- TEAEs resulting in reduction or interruption of study medication;
- Time to the first TEAE that results in a reduction or interruption of study drug.

The incidence of TEAEs will be summarized by relationship to study drug according to the following categories: "treatment-related," or "not treatment-related". If a patient experiences multiple occurrences of the same AE with different relationship categories, the patient will be counted once, as a relationship category of treatment related.

If a patient experiences multiple occurrences of the same AE with different toxicity grades, the patient will be counted once for the maximum (most severe) toxicity grade. AEs with a missing toxicity grade will be presented in the summary table with a toxicity grade of "Missing." For each toxicity grade, the number and percentage of patients with at least one TEAE of the given maximum grade will be summarized.

The time to the first TEAE and first treatment-related TEAE that results in a dose reduction, delay, interruption, or discontinuation of study drug is defined as 1+ the number of days from the first dose of study drug to the start of the first adverse event. The cumulative incidence is presented in a 1-KM graph for just the patients with an event and the median time to onset will be calculated together with the 95% CI.

Non-TEAEs (pre-treatment and post-treatment) will be presented in the by patient data listings for the safety population.

MedDRA PTs were combined for the following similar terms:

- Asthenia/Fatigue
- Alanine Aminotransferase (ALT)/ Aspartate Aminotransferase (AST) Increased
- Anaemia and/or Low/Decreased Haemoglobin
- Thromobocytopenia and/or Low/Decreased Platelets
- Neutropenia and/or Low/Decreased Absolute Neutrophil Count (ANC)

In addition, the analysis of combined terms for anemia is explored as a time to first event analysis as described above. Transfusions (blood or plasma) and concomitant medications / growth factor support are provided in patient listings. The number of transfusions and the time to fist transfusion is also summarized.

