### **5.1.4 Treatment Discontinuation**

Upon treatment discontinuation, regardless of reason, patients will have a Treatment Discontinuation visit. Assessments at this visit will include AEs, serum pregnancy for women of child-bearing potential, disease status assessment, and study drug accountability; in addition, complete blood count, clinical chemistry, urinalysis, and vital signs may be performed per local standard of care practices. An optional tumor biopsy will be collected from patients who experience disease progression and provide appropriate consent prior to the start of any subsequent anticancer treatment. If disease progression is caused by appearance of a new lesion(s), the lesion(s) should be prioritized for the optional biopsy. All patients discontinued from treatment will be followed for 28 days following the last dose of study drug for the collection of AEs.

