### **8.1 Anticancer or Experimental Therapy**

No anticancer therapy is permitted to have been administered as maintenance treatment in the interval period between completion of the most recent platinum-based chemotherapy and initiation of maintenance treatment in this study.

No other anticancer therapies (including chemotherapy, radiation, hormonal treatment, antibody or other immunotherapy, gene therapy, vaccine therapy, angiogenesis inhibitors, or other experimental drugs) of any kind will be permitted while the patient is participating in the study, with the exception of ongoing hormonal treatment for previously treated breast cancer.

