#### **9.4.2 28-day Follow-up**

The following procedures will be performed for all patients at 28 ( $\pm 3$ ) days after the last dose of study drug:

- Disease assessment for patients who discontinued treatment for reason other than disease progression or death. Tumor scans should continue to be performed at 12-week intervals (up to 7 days prior permitted) until radiologic disease progression by RECIST v1.1, as assessed by the investigator. Patients who have been on study at least 18 months may decrease the frequency of disease assessments to every 16 ( $\pm 2$ ) weeks. Investigator should consult with sponsor's medical monitor before decreasing frequency.
- AE monitoring (only SAEs/AESIs are recorded through 28 days after last dose of rucaparib. Ongoing SAEs and AESIs will be followed until resolution, stabilization, or lost to follow-up).
- Subsequent treatments, secondary malignancy monitoring, and overall survival (OS)

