### ***10.7.2 Causal Relationship of Adverse Events to Study Drug***

Medical judgment should be used to determine the cause of the AE considering all relevant factors such as, but not limited to, the disease under study, concurrent disease, concomitant medication, relevant history, pattern of the AE, temporal relationship to the study medication, dechallenge or rechallenge with the study drug.

Not Related To Study Drug	An AE that is clearly due to extraneous causes (eg, concurrent disease, concomitant medication, disease under study, etc.) An AE that does not follow a reasonable temporal sequence from administration of the study drug. An AE that does not follow a known pattern of response to study drug. An AE that does not reappear or worsen when study drug is restarted. An AE for which an alternative explanation is likely, but not clearly identifiable.
---------------------------	--

Related to Study Drug	An AE that is difficult to assign to alternative causes. An AE that follows a strong or reasonable temporal sequence from administration of study drug. An AE that could not be reasonably explained by the patient's clinical state, concurrent disease, or other concomitant therapy administered to the patient. An AE that follows a known response pattern to study drug. An AE that is confirmed with a positive rechallenge or supporting laboratory data.
-----------------------	---

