10 EFFICACY ANALYSIS

10.1 Primary Efficacy Analysis

The primary efficacy endpoint is PFS as assessed by the investigator (invPFS). The time to invPFS will be calculated in months as the time from randomization to disease progression +1 day, as determined by RECIST v1.1 criteria² or death due to any cause, whichever occurs first.

Only scans and deaths prior to the start of any subsequent anti-cancer treatment or within 90 days of treatment end date will be included in the analysis. Patients without a documented event of progression will be censored on the date of their last tumor assessment (i.e., radiologic assessment) prior to the start of any subsequent anti-cancer treatment or within 90 days of treatment end date. Patients who withdrew without a disease progression event and do not have any post-baseline tumor assessment will be censored at date of randomization.

The stratified log rank test will be considered the primary analysis for invPFS comparing rucparib to placebo. In addition, a stratified Cox proportional hazard model will be used to calculate the hazard ratio (HR) between the treatment groups. The following randomization strata are used to estimate the treatment effect:

- HRD classification by the CTA (tBRCA, nbHRD, biomarker negative)
- Best response to most recent platinum-based regimen (CR, PR)
- Interval between completion of the penultimate platinum-based regimen and disease progression (6 to 12 months or > 12 months)

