12.2 Clinical Laboratory Evaluations

Clinical laboratory evaluations include the continuous variables for hematology, serum chemistry, and urinalysis. The laboratory values will be presented in SI units. The on-treatment period will be defined as the time from randomization to 28 days after the last dose of study drug. Laboratory values collected during the on-treatment period will be included in the summary tables. The laboratory values collected after the on-treatment period will only be presented in the data listings.

The summary of laboratory data will include descriptive statistics (N, mean, SD, minimum, median, and maximum) of the maximum, minimum, and last value during the on-treatment period. Summaries using descriptive statistics of the change from baseline to the maximum, minimum, and last value during the on-treatment period will also be given.

Summary tables from baseline to the maximum on-treatment toxicity grade (CTCAE Version 4.03) for each lab parameter will be summarized. In addition, the number and percent of patients who has at least one worsening in toxicity grade on-treatment compared to baseline toxicity grade will be summarized by treatment group.

Laboratory data including normal ranges and flagged abnormal laboratory findings will be provided using by-patient listings.

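### The adverse-event, laboratory and vital-sign windows run to last dose plus 28 days without stopping at the next anticancer therapy, so toxicity of that therapy can enter the safety tables in both arms

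*SAP*

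**What the plan says.** SAP 12.1 defines a TEAE by onset date alone, from first dose "until the date of the last study medication dose plus 28 days"; protocol 11.2.5.1 has the same end. For laboratory values SAP 12.2 states: "The on-treatment period will be defined as the time from randomization to 28 days after the last dose of study drug". SAP 12.3 repeats this for vital signs. None of these sections mentions subsequent anticancer therapy.

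Protocol 5.1.4 matches collection to the window: "All patients discontinued from treatment will be followed for 28 days following the last dose of study drug for the collection of AEs". Protocol 5.1.3 takes patients off study drug at investigator-assessed progression, and protocol 9.4.2 has subsequent treatments recorded at the 28-day visit. No minimum interval before the next therapy is stated.

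Two provisions bear on how such events are read:

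- **Causality.** SAP 12.1 plans a treatment-related table and states: "The incidence of TEAEs will be summarized by relationship to study drug according to the following categories" treatment-related or not. Protocol 10.7.2 tells investigators to class events clearly due to other causes as not related.
- **Efficacy.** SAP 10.1 does refer to new therapy for invPFS. It uses scans and deaths "prior to the start of any subsequent anti-cancer treatment", but joins this by *or* to a second condition, within 90 days of treatment end.

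**The concern.** The 28-day tail is there to catch late effects of study drug. Once a new regimen starts inside it, the tables cannot tell the two sources apart. Protocol 3.3.2.1.1 reports nausea, vomiting, fatigue and myelosuppression with rucaparib, and protocol 3.3.2.1.2 reports the gastrointestinal events and fatigue again. Chemotherapy can be expected to cause events of the same kind, although the documents give no rates for it.

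At stake is the comparison of TEAE percentages between arms. Each patient counts once per term, so a new event matters most where few patients already have that term. If placebo patients progress sooner and start with a lower rate of the terms typical of rucaparib, the next therapy adds more percentage points to placebo, and the rucaparib excess looks smaller than it is. Counting each patient at maximum grade adds a second route: a mild event on study drug can be replaced by a more severe event of the same term under the next regimen.

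**Working it through.** The plan states no figure for this, so there is none to reproduce. The check has a textual part and an illustrative part.

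**1. Which outputs are exposed**

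- The all-TEAE, by-grade, Grade 3 or higher, serious and fatal tables in SAP 12.1 use onset date only and are exposed.
- Laboratory and vital-sign summaries use the minimum, maximum and last on-treatment value, and laboratory data also the maximum toxicity grade. They carry no causality judgment, so any value drawn in the tail after new therapy counts.
- The treatment-related table is exposed only if the investigator misjudges cause.
- The tables of discontinuation, reduction and interruption depend on action taken with study drug, so events after the last dose hardly reach them.

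**2. Share of each arm that has opened a 28-day tail by progression**

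Inputs from SAP 2.3: ITT median PFS 6 months (placebo) and 8.5 months (rucaparib), 2:1 allocation, N = 540, 70% events. Assumptions: exponential PFS and a common follow-up time t. Solve

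(1/3)(1 − e^(−t·ln2/6)) + (2/3)(1 − e^(−t·ln2/8.5)) = 0.70, which gives t = 13.19 months.

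- Placebo: 1 − e^(−13.19·ln2/6) = 0.782
- Rucaparib: 1 − e^(−13.19·ln2/8.5) = 0.659
- Ratio: 0.782/0.659 = 1.19

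With 24-month uniform accrual (assumed) the shares are 77.0% and 66.5%. With the tBRCA medians (6 and 12 months) they are 85.7% and 62.2%. In patients, 2:1 allocation reverses the order: 180 × 0.782 ≈ 141 placebo and 360 × 0.659 ≈ 237 rucaparib. These shares are approximate, because PFS events include deaths, and patients who stop for other reasons also have a tail.

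**3. Illustrative effect on one term**

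Reported incidence = b + (1 − b)·p·w·c, where b is true incidence, p the progressed share from step 2, w the share of those starting new therapy within 28 days, and c the probability of the event in the rest of the window. The values b = 5% (placebo) and 35% (rucaparib), w and c are all assumed, with w and c equal across arms.

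For w = 0.20 and c = 0.30:

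- Placebo: 0.05 + 0.95 × 0.782 × 0.06 = 0.095
- Rucaparib: 0.35 + 0.65 × 0.659 × 0.06 = 0.376

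| w | c | Placebo % | Rucaparib % | Difference (true 30) | Ratio (true 7.0) |
|---|---|---|---|---|---|
| 0.10 | 0.30 | 7.2 | 36.3 | 29.1 | 5.0 |
| 0.10 | 0.50 | 8.7 | 37.1 | 28.4 | 4.3 |
| 0.20 | 0.30 | 9.5 | 37.6 | 28.1 | 4.0 |
| 0.20 | 0.50 | 12.4 | 39.3 | 26.9 | 3.2 |
| 0.40 | 0.30 | 13.9 | 40.1 | 26.2 | 2.9 |
| 0.40 | 0.50 | 19.9 | 43.6 | 23.7 | 2.2 |

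**4. Dependence on the assumed base rates**

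With w = 0.30 and c = 0.50 (w·c = 0.15), points added are 100·(1 − b)·p·0.15:

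- b = 20% and 50%: 9.4 placebo, 4.9 rucaparib
- b = 30% in both arms: 8.2 and 6.9
- b = 90% and 98%: 1.2 and 0.2

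Both arms rise in every case. The gap between them depends mostly on base rates that the documents do not give.

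**The case against.** Protocol 8.1 says that no other anticancer therapy "of any kind will be permitted while the patient is participating in the study", which read literally would keep new therapy out of the window. It cannot extend to follow-up, because protocol 5.1.5 and 9.4.2 collect subsequent treatments there.

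A fixed tail treats both arms alike and matches the collection period, whereas cutting at new therapy conditions on an event after randomization that is linked to progression and shortens observation differently by arm. That stands, and is a reason to add the truncated tables and not to replace the full ones.

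The laboratory part is less certain. The current schedule lists no laboratory tests at the 28-day visit. Protocol 12.2 does place the Treatment Discontinuation visit 28 (±3) days after the last dose, and protocol 9.4.1 advises hematology and chemistry there. The schedule in force when the SAP was written is not shown in the current protocol.

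A reader might infer four stronger things that the documents do not support:

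- **That these events are attributed to study drug.** A TEAE is defined by time, and the SAP reports relatedness separately.
- **That the bias falls mainly on placebo.** Both arms are affected and more rucaparib patients have a tail. The design medians alone give a ratio of only 1.19.
- **That the SAP cleanly cuts efficacy data at new therapy.** The 90-day alternative in SAP 10.1 can, as worded, admit later scans.
- **That the risk ratio collapses.** The fall from 7.0 to 3 or 4 comes largely from the chosen 5% base.

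Rucaparib patients are also expected to stay on treatment longer, which raises their crude incidence. The net direction of all influences on the tables is therefore not settled here.

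**Conclusion.** The gap is real and lies in the text: no safety window stops at subsequent anticancer therapy, and such therapy can start inside it while adverse events are still being collected. How often it does is not stated. For terms more common on rucaparib, the tail probably adds somewhat more percentage points to placebo, so this mechanism slightly understates the excess. That assumes similar early-start and event rates in the two arms.

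The size cannot be determined from the documents. In the 5% versus 35% illustration the risk difference falls by about 2 to 3 points when 20% start within 28 days, and by 0.9 to 6.3 points over 10–40%. This affects how the safety tables are read, not the efficacy result, and merits a supplementary analysis.

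**What to change.** - Produce the TEAE tables and the on-treatment laboratory and vital-sign tables with a window that ends at the earlier of last dose plus 28 days or the day before the first subsequent anticancer therapy.
- Keep the full 28-day tables alongside, with SAEs and AESIs over the full window. Protocol 3.3.2.1.1 notes that myelosuppression may be delayed, so late drug effects must stay visible.
- Flag, by arm, events with onset after new therapy began, and report how many patients in each arm started new therapy within the 28 days. That replaces the assumed rate of early starts with data.

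The cost is SAP wording, one derived date and additional tables. SAP 10.4.9 already needs the start date of the first subsequent therapy. SAP 12.1 lists no AESI table, so that output would be new. Because the full-window tables stay, the windows in protocol 11.2.5.1 to 11.2.5.3 are still honored. The downside is that a drug-related event first seen after new therapy appears only in the full-window tables.

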--	--

	
of contraception (failure rate < 1% per year) with their male partners during treatment and for 6 months following the last study drug dose.
 
No waivers of these inclusion or exclusion criteria will be granted by the investigator and the sponsor or its designee for any patient enrolled into the study.

Study Treatment	
Eligible patients will be randomized 2:1 to receive rucaparib (600 mg twice a day [BID]) or placebo. Randomization will occur by a central randomization procedure using an Interactive Voice Response System/Interactive Web Response System (IVRS/IWRS). The following will be included as randomization stratification factors at study entry to ensure treatment groups are balanced:
 
 
• HRD classification (tBRCA, nbHRD, or biomarker negative) by the ICTA (Appendix A).
 
• Interval between completion of the penultimate platinum-based regimen and disease progression (6 to 12 or >12 months) by radiologic assessment
 
• Best response to the most recent platinum-based regimen (CR [defined as complete radiologic response by RECIST or PR [defined as partial response by RECIST and/or a GCIG CA-125 response]). All responses require that CA-125 be <ULN.
 
 
Randomization to study treatment must occur within 8 weeks following a patient's last dose of platinum-based chemotherapy. Study drug will be taken orally twice daily (12 hours apart) with at least 8 oz (240 mL) of water. Study drug may be taken with an empty stomach or with food.
 
Patients will take study drug twice daily for continuous 28-day cycles until disease progression by RECIST as assessed by the investigator, or other reason for discontinuation. Treatment interruptions and/or dose reductions are permitted in the event of unacceptable toxicity.

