#### **11.2.5.1 Adverse Events**

AEs will be classified using the Medical Dictionary for Drug Regulatory Activities (MedDRA) classification system. The severity of the toxicities will be graded according to the NCI-CTCAE whenever possible. Only treatment-emergent adverse events (TEAEs) will be collected: TEAEs are defined as AEs with onset date on or after the date of first dose of study medication until the date of the last study medication dose plus 28 days.

The number and percentage of patients who experienced TEAEs for each system organ class (SOC) and preferred term will be presented. Multiple instances of the TEAE in each SOC and multiple occurrences of the same preferred term are counted only once per patient. The number and percentage of patients with at least one TEAE will also be summarized.

Separate tables will be presented as follows:

- All TEAEs
- TEAEs by CTCAE grade
- Grade 3 or greater TEAEs
- Serious TEAEs
- TEAEs with an outcome of death
- TEAEs leading to discontinuation of study medication
- TEAEs resulting in interruption/delay of study medication
- TEAEs resulting in dose reduction of study medication

If a patient experiences multiple occurrences of the same AE with different toxicity grades, the patient will be counted once for the maximum (most severe) toxicity grade. AEs with a missing toxicity grade will be presented in the summary table with a toxicity grade of "Missing." For each toxicity grade, the number and percentage of patients with at least one TEAE of the given grade will be summarized.

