2.3 Sample Size

Approximately 540 patients will be randomized (2:1) to receive either rucaparib or placebo in this study. A minimum of 180 and a maximum of 200 patients with a deleterious tBRCA mutation will be enrolled. Enrollment of patients with a known deleterious germline *BRCA1/2* mutation (gBRCA) documented in their medical record will not exceed 150. There is no minimum number of patients required for each of the nbHRD and biomarker negative subgroups; however, no more than 360 total patients will be randomized for stratification into these subgroups combined.

Tumor HRD status by the CTA (see Section 3.2) will be determined after randomization, but before the final efficacy analysis, so that the primary endpoint (PFS in molecularly-defined HRD subgroups) can be assessed prospectively.

Group	Hazard Ratio	Cumulative N	Minimum Number of Events (70%)	Median PFS Placebo vs Rucaparib (months)	Power	One- sided Alpha
tBRCA	0.50	180	126	6 vs 12	90%	0.025
HRD	0.60	300	210	6 vs 10	90%	0.025
ITT	0.70	540	378	6 vs 8.5	90%	0.025

The study will end after 70% of the patients in the tBRCA subgroup have an observed event of investigator-determined disease progression or death. If the minimum number of tBRCA patients are enrolled, then the study will end following the 126th event of investigator-determined disease progression or death. Similarly, if the maximum number of tBRCA patients are enrolled then the study will end following the 140th event of investigator-determined disease progression or death. The Independent Data Monitoring Committee (IDMC) will inform the sponsor when the required number of PFS events have been observed in order to ensure the sponsor remains blinded to which patients are in the tBRCA subgroup.

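### Crude adverse-event percentages cover a longer window on rucaparib (about 1.4 times in the safety population), and the graph called cumulative incidence leaves out event-free patients

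*SAP*

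**What the plan says.** SAP 12.1 summarizes treatment-emergent adverse events (TEAEs) by system organ class and preferred term: "The number and percentage of patients who experienced TEAEs for each SOC and PT will be presented". Protocol 11.2.5.1 has the same measure: "The number and percentage of patients who experienced TEAEs for each system organ class (SOC) and preferred term will be presented". Each patient counts once per term ("multiple occurrences of the same PT are counted only once per patient"), and an event is treatment-emergent if it starts between first dose and the end of follow-up, which lasts "until the date of the last study medication dose plus 28 days".

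The length of that window depends on time on drug. The protocol synopsis says: "Patients will take study drug twice daily for continuous 28-day cycles until disease progression by RECIST as assessed by the investigator", or until another reason for stopping. SAP 2.3 assumes median PFS, placebo vs rucaparib, of 6 vs 12 months (tBRCA), 6 vs 10 (HRD) and 6 vs 8.5 (ITT).

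SAP 12 runs the safety analyses on the safety population, and SAP 12.4 explores safety further in tBRCA and HRD. SAP 7 summarizes treatment duration but does not use it as a denominator for adverse events.

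SAP 12.1 also plans time to first TEAE, and first treatment-related TEAE, leading to dose modification or discontinuation. For these, "The cumulative incidence is presented in a 1-KM graph for just the patients with an event". Combined-term anemia is analysed in the same way. Time to first transfusion is summarized with no method given. Neither document plans a person-time rate or incidence at a fixed time.

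**The concern.** Safety is a secondary objective, with incidence of adverse events as an endpoint, and the tables put the arms side by side. If rucaparib delays progression as planned, its patients are observed for TEAEs for longer. An event occurring at the same monthly rate in both arms will then appear in a higher percentage of rucaparib patients, and a reader of the crude table cannot tell longer observation from a higher rate.

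The graph should separate the two but cannot. Once event-free patients are removed, everyone left has an event, so one minus Kaplan-Meier climbs to 100% in each arm whether 5% or 60% of the arm was affected. It shows when onset occurred among those affected. It does not estimate incidence.

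**Working it through.** **1. The plan's own figures.** For the ITT row (HR 0.70, 378 events, 2:1, one-sided 0.025), the Schoenfeld formula gives √(378 × 2/3 × 1/3) × |ln 0.70| − 1.96 = 9.165 × 0.3567 − 1.96 = 1.309, a power of 90.5% against the stated 90%. The median ratios 6/12 = 0.50, 6/10 = 0.60 and 6/8.5 = 0.706 match the stated hazard ratios, so the medians fit an exponential model.

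**2. Mean time at risk.** Assume exponential time on drug with median m equal to the planned median PFS. Add 28/30.4375 = 0.92 months for the tail. Mean = m/ln 2 + 0.92.

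| Arm | Median (months) | Mean at risk (months) | Ratio to placebo |
|---|---|---|---|
| Placebo | 6 | 9.6 | – |
| Rucaparib, ITT | 8.5 | 13.2 | 1.38 |
| Rucaparib, HRD | 10 | 15.3 | 1.60 |
| Rucaparib, tBRCA | 12 | 18.2 | 1.90 |

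**3. Crude percentage with the same hazard in both arms.** The documents give no event hazards, so a range of λ is assumed. With μ = ln 2/m, crude % = 1 − [μ/(μ+λ)] × exp(−0.92λ). Example, λ = 0.05, placebo: μ = 0.1155, and 1 − (0.1155/0.1655) × 0.955 = 33.3%.

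| λ per month | Placebo | Rucaparib, ITT medians | Rucaparib, tBRCA medians |
|---|---|---|---|
| 0.01 | 8.8% | 11.7% (+2.9) | 15.5% (+6.7) |
| 0.02 | 16.3% | 21.2% (+4.8) | 27.1% (+10.8) |
| 0.05 | 33.3% | 40.8% (+7.5) | 48.8% (+15.5) |
| 0.10 | 51.1% | 59.0% (+7.9) | 66.6% (+15.5) |
| 0.20 | 69.5% | 75.9% (+6.4) | 81.4% (+11.8) |

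Between the tabulated values the gap peaks at 8.0 points (ITT, λ near 0.08) and 16.0 points (tBRCA, λ near 0.07).

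**4. What reduces the gap.** With an assumed 18-month limit on observation, the gaps over the same hazards are 1.6 to 6.7 points (ITT) and 3.1 to 12.7 (tBRCA). At λ = 0.5, where nearly everyone has the event, the ITT gap is 3.0 points. For an event possible only in the first month it is 0.0.

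**5. Incidence at fixed times, event-free patients kept.** With the end of the TEAE window as a competing event, and u = t − 0.92, cumulative incidence at month t = 1 − exp(−0.92λ) × {[μ/(μ+λ)] × (1 − e^(−(μ+λ)u)) + e^(−(μ+λ)u)}. At λ = 0.05:

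| Month | Placebo | Rucaparib, ITT medians | Rucaparib, tBRCA medians |
|---|---|---|---|
| 3 | 12.9% | 13.2% (+0.3) | 13.4% (+0.5) |
| 6 | 20.9% | 22.2% (+1.3) | 23.2% (+2.3) |
| 12 | 28.7% | 32.3% (+3.6) | 35.4% (+6.6) |

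The gap is small early and grows with time, and the table shows the reader where it comes from.

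**6. Rate per patient-year.** With equal constant hazards this gives 24, 60 and 120 first events per 100 patient-years in both arms for λ = 0.02, 0.05 and 0.10, a ratio of 1.00. It misleads for early events. Take an assumed first-month event in 20% of placebo and 30% of rucaparib patients (risk ratio 1.5), with onset at half a month on average. Person-months per patient are 0.8 × 9.6 + 0.2 × 0.5 = 7.78 on placebo. On rucaparib they are 0.7 × 18.2 + 0.3 × 0.5 = 12.89 (tBRCA) or 0.7 × 13.2 + 0.3 × 0.5 = 9.39 (ITT). The rate ratio is (0.30/12.89)/(0.20/7.78) = 0.9 or (0.30/9.39)/(0.20/7.78) = 1.2, so a real excess is diluted or reversed.

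**The case against.** The strongest reply is that crude incidence is a legitimate measure. Longer treatment follows from assignment in a randomized trial, and the percentage affected over the treatment course is what a patient faces. The tables are descriptive, no test of adverse events is specified, and any artefact runs against rucaparib, so it does not hide harm. Treatment duration is tabulated, so readers will see that exposure differs. All of this stands. It is why the crude tables should stay and why no efficacy conclusion is affected. It does not let a reader judge how much of a given difference is due to exposure.

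Some stronger readings are tempting, but the documents do not support them:

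- *Rucaparib patients are on drug twice as long.* That ratio of medians is the tBRCA assumption only. The main tables use the whole safety population, where it is 8.5/6 = 1.42.
- *Every equal-rate event will look like excess toxicity.* Protocol 3.3.2.1.1 places ALT/AST elevations in the first 2 to 4 weeks, where extra exposure adds almost nothing. The same section says myelosuppression may be delayed, so the point does apply to three of the SAP's five combined terms: anemia, thrombocytopenia and neutropenia.
- *Nothing but crude counts is planned.* Time-to-first-event, anemia and transfusion summaries are planned. The restriction to patients with an event is written for the TEAE graph and carried over to anemia. It is not stated for transfusion.

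**Conclusion.** The point holds in a limited form. TEAE incidence is tabulated only as crude percentages over a window that the plan's assumptions make about 1.4 times longer on rucaparib in the safety population, and up to about 1.9 times longer in the exploratory tBRCA tables. For events that keep accruing, the same rate in both arms would appear as a rucaparib excess of about 3 to 8 points, or 7 to 16 in tBRCA. Separately, the graph labelled cumulative incidence is wrong as written, whatever the exposure.

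The sizes rest on assumptions that are not in the documents: constant and equal hazards of 0.01 to 0.20 per month, exponential time on drug, and time on drug equal to planned PFS. Stopping for toxicity would shorten rucaparib exposure and narrow the gap, as would a data cut-off. This should be changed. It affects how the safety tables are read, not any formal test.

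**What to change.** - Compute the time-to-first-TEAE and anemia curves by arm on all safety-population patients. Keep event-free patients in the risk set, treat the end of the TEAE window (discontinuation or death) as a competing event, and treat data cut-off as censoring.
- Report cumulative incidence by arm at fixed times, for example 3, 6 and 12 months, for all, Grade 3 or higher, serious and combined-term TEAEs. Do this in the safety population and in the tBRCA and HRD safety subgroups. This should be the main addition.
- Keep the crude tables. Add first events per 100 patient-years at risk as a supplement, with a note that it assumes a roughly constant hazard and dilutes early-onset toxicity.
- If the event-only display is kept, label it as time to onset among affected patients.

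The cost is a few extra tables and revised graphs. The inputs (onset, first-dose and last-dose dates) are already needed for the TEAE and treatment-duration definitions, so no new data are collected.
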